4.3.3. Dose Limiting Toxicity Definition

For the purpose of dose escalation, any of the following AEs will be classified as DLTs:

- Occur in the first cycle of treatment, or within 28 days after the start of the study treatment; and
- Are at least possibly related to PF-07209960; A participant is classified as DLT evaluable if he/she experiences a DLT or if he/she otherwise in the absence of a DLT receives 2 doses of the study intervention during Cycle 1 and has received all scheduled safety assessments during the DLT window. If a participant fails to meet these criteria, he/she may be replaced. Monitoring for DLTs will occur during Part 1.

Significant AEs considered to be related to the study intervention or treatment under investigation that occur after the DLT observation period will be reviewed in context of all safety data available. That review may result in re-evaluation of the dosing level or regimen.

Hematologic DLTs:

1. Grade 4 neutropenia (absolute neutrophil count [ANC] <500/mm³) lasting >7 days;
2. Febrile neutropenia (defined as an ANC <1000/mm³, with a single temperature of >38.3°C [101°F], or a sustained temperature of ≥38°C [100.4°F] for more than one hour);
3. Neutropenic infection (defined as an ANC <1000/mm³ with Grade ≥3 infection);
4. Grade 3 thrombocytopenia (platelet count <50,000 mm³) with any bleeding;
5. Grade 4 thrombocytopenia (platelet count <25,000/mm³);
6. Grade 4 anemia (life-threatening consequences; urgent intervention indicated).

Non-Hematologic DLTs:

- Any Grade ≥3 non-hematologic treatment related AE is a DLT with the following exceptions:
 1. Grade 3 nausea, vomiting, diarrhea, or fatigue that can be controlled with or without medical therapy to Grade ≤2 within 72 hours;
 2. Grade ≥3 laboratory abnormalities without a clinical correlate and that do not require medical intervention, or are corrected to Grade ≤2 with supplementation/appropriate management within 72 hours;

Immune-related AE (irAE) that meet the following criteria:

1. Grade 4 irAE regardless of duration (for lab abnormalities without clinical correlate and do not require medical intervention please refer to criteria above);

2. Grade ≥ 3 colitis regardless of duration (diagnosis of colitis must be supported by diagnostic testing);
3. Grade ≥ 3 non-infectious pneumonitis regardless of duration;
4. Grade 2 non-infectious pneumonitis that does not resolve to \leq Grade 1 within 72 hours of the initiation of maximal supportive care;

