5. Any grade immune-mediated myocarditis;
6. Grade 3 irAE, excluding colitis and pneumonitis, that does not improve to \leq Grade 2 within 72 hours after onset of the AE event despite maximal supportive care including systemic corticosteroids or downgrade to \leq Grade 1 or baseline within 14 days;
7. Grade ≥ 3 immune-related endocrinopathies (eg, thyroid disorders, diabetes mellitus, adrenal insufficiency) that require treatment discontinuation or are not successfully managed with hormonal replacement therapy.

Other cases that meet the following DLT criteria:

1. Hy's Law cases defined as: ALT or AST $>3 \times$ ULN if normal at baseline OR $>3 \times$ ULN and doubling the baseline (if $>$ ULN at baseline) associated with total bilirubin $>2 \times$ ULN and an alkaline phosphatase $<2 \times$ ULN.
2. A treatment related AE inducing a delay by ≥ 4 weeks in receiving the next scheduled cycle due to persisting toxicities attributable to PF-07209960 will be considered a DLT.
3. Clinically important or persistent toxicities (eg, toxicities responsible for significant dose delay) that are not included in the above criteria may also be considered a DLT following review by the investigators and the sponsor. All DLTs need to represent a clinically significant shift from baseline. While the rules for adjudicating DLTs are specified above, an AE not listed above, or an AE meeting the DLT criteria above but occurring outside of the DLT observation period may be defined as a DLT following assessment, based on the emerging safety profile.

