6.1.1. Dose-Limiting Toxicities (DLTs)

- Analysis set: Per protocol analysis set
- Analysis methodology:

For the purpose of dose escalation, the DLT observation period/window will be the first cycle (defined as 28 days after the start of study treatment), for each participant. Whether an adverse event a participant experienced during the DLT window is determined as a DLT or not is based on the DLT definitions provided in Section 4.3.3 of the protocol.

The DLT events will be summarized by dose level. A listing of the DLT events will also be provided in which the participant's primary diagnosis (malignancy), dose level the participant was enrolled to, DLT event start day and stop day relative to the C1D1 dose date, the DLT event term, NCI CTCAE grade, relatedness to the investigational product (PF-07209960), outcome of the event, along with other variables deemed important, will be included.

- Missing data: All enrolled participants in Part 1 should have an indicator variable derived to be either 1 (yes) or 0 (no) based on the DLT definitions (provided in

Section 4.3.3 of the protocol) and participant's safety data during the DLT observation window. If a participant fails to have a value on the indicator variable because the participant being non-DLT-evaluable, the participant may be replaced.

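### SAP 6.1.1 scores DLTs from 28-day data, but some Protocol 4.3.3 criteria for in-window events can be met only after Day 28

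*Protocol*

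**What the plan says.** Protocol 4.3.3 defines a DLT as an AE that occurs in the first cycle (28 days), is at least possibly related to PF-07209960, and meets any listed criterion. Some criteria are settled at onset: any Grade 3 or higher "non-hematologic treatment related AE is a DLT with the following exceptions", the two exceptions being short-lived gastrointestinal events or fatigue, and laboratory changes. Others need time to run:

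- Grade 4 neutropenia counts only if it lasts more than 7 days.
- irAE item 6 counts a "Grade 3 irAE, excluding colitis and pneumonitis, that does not improve to" Grade 2 or lower within 72 hours, or to Grade 1 or baseline within 14 days.
- A related AE that causes a delay of at least 4 weeks "in receiving the next scheduled cycle due to persisting toxicities attributable to PF-07209960 will be considered a DLT".

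A participant is evaluable if he or she has a DLT, or "in the absence of a DLT receives 2 doses of the study intervention during Cycle 1" and has had all scheduled safety assessments in the window.

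SAP 6.1.1 defines the window as the first cycle, 28 days from the start of treatment. Under its missing-data bullet, all enrolled Part 1 participants "should have an indicator variable derived to be either 1 (yes) or 0 (no) based on the DLT definitions" in Protocol 4.3.3 and on the participant's safety data within that window.

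**The concern.** The definition and the data rule do not match. Protocol 4.3.3 fixes when the AE must occur. SAP 6.1.1 restricts the data used to score it. If the deciding fact comes after Day 28, an indicator built only from window data cannot record it. A participant who has had both Cycle 1 doses and the scheduled assessments is evaluable, so the result is a 0, not a missing value or a replacement.

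First-cycle DLT is a Part 1 primary endpoint and the only outcome in the BLRM. Cohorts are about 2-4 participants, so one event matters. Later model runs can be corrected if someone recodes the event, but the next cohort may already have been dosed. The error runs in one direction, towards too few DLTs.

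**Working it through.** The plan states no figure on this point, so there is nothing to reproduce. The check is day arithmetic on the criteria, then one worked case.

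**Inputs.** C1D1 is Day 1 and the window is Days 1-28 (Protocol 4.3.3; SAP 6.1.1). Doses fall on Days 1 and 15 of a 28-day cycle, so C2D1 is Day 29. Let d be the onset day.

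| Criterion | Condition to be settled by Day 28 | Open onsets |
|---|---|---|
| Cycle 2 delayed at least 4 weeks | earliest day met = 29 + 28 = 57 | Days 1-28 (28 of 28) |
| Grade 4 neutropenia >7 days, elapsed count | d + 7 < 28, so d ≤ 20 | Days 21-28 (8 of 28) |
| Same, calendar count (Days 21-28 are 8 days) | d ≤ 21 | Days 22-28 (7 of 28) |
| irAE item 6, 14-day test | d + 14 ≤ 28, so d ≤ 14 | Days 15-28 (14 of 28) |
| 72-hour tests | d + 3 ≤ 28, so d ≤ 25 | Days 26-28 (3 of 28) |

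These counts are onset days, not shares of events.

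**Where item 6 decides.** A clinical Grade 3 irAE outside the two exceptions is already a DLT at onset under the general rule. Item 6 matters only for events that the exceptions release. An example is an immune Grade 3 transaminase rise with no clinical correlate that falls to Grade 2 within 72 hours but has not reached Grade 1 or baseline by 14 days. So 14 of 28 applies to a narrow group.

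**Worked case for the delay criterion.** Grade 3 thrombocytopenia is a DLT only with bleeding, and Grade 4 starts below 25,000/mm³ (Protocol 4.3.3). Retreatment needs at least 50,000/mm³ (Protocol 6.6.2). Suppose a participant receives both Cycle 1 doses, then falls between these limits late in the cycle without bleeding and stays there.

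1. On Day 28 no listed objective criterion is met. The participant is evaluable, and SAP 6.1.1 gives 0.
2. On Day 29 Cycle 2 is held.
3. If the hold reaches Day 57, Protocol 4.3.3 makes the event a DLT.
4. Window data still give 0.

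**What one recoded event can do.** Without any prior, a first DLT in the current cohort lowers the escalation cap from half-log (about ×3.2) to 100% (×2) under Protocol 4.3.2, although the sponsor may later restore it. For the model, the trial's priors are not shown, so this is illustration only. The assumptions are a two-parameter logistic model with log(α) SD 2, a prior mean of 33%, 20% or 10% at the reference dose, log(β) ~ N(0,1), and 0/3 at 0.1 and 0.316 times the current dose. The quantity is P(DLT rate ≥ 0.33), against the 25% limit in Protocol 4.3.2.

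- Current dose, reference dose equal to it: 0/3 gives 0.02-0.06 and 1/3 gives 0.20-0.33, above 25% under 2 of 3 priors. 1/4 gives 0.14-0.24, never above.
- Twice the current dose, reference dose 3.16 or 10 times current: 0/3 gives 0.01-0.10 and 1/3 gives 0.13-0.44, above 25% in 4 of 6 settings. 1/4 gives 0.10-0.38, above in 2 of 6.
- Reference dose equal to the current dose: doubling after 0/3 already gives 0.315, 0.258 and 0.196, so a 0 does not always permit the step.

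One recoded event can therefore change a dose decision in some settings and not in others.

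**The case against.** The best reply is that the plan already works by onset. Protocol 4.3.3 and SAP 3.5.1 speak of AEs that occur in the window. SAP 6.1.1 points back to 4.3.3, lists each DLT's stop day and outcome, and states no Day 28 data lock. Protocol 8.3.3 requires AEs to be followed to resolution or stabilization.

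There are also safeguards:

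- The third of the other DLT criteria in Protocol 4.3.3 lets investigators and sponsor call a persistent toxicity behind a significant dose delay a DLT, without waiting for Day 57.
- The same paragraph lets an AE outside the window be called a DLT.
- A BLRM sensitivity run weights equivocal events at 0.5 (Protocol 9.4.1.1, Appendix 8).
- The dose level review may choose a lower dose or delay dosing (Protocol 9.6).

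Much of this stands. Onset is the sensible reading, and a team using these powers well would catch many cases. But the only sentence on how the indicator is built ties it to window data. The first two clauses are optional, and the second concerns AEs arising outside the window, not those that start inside and resolve later. The weighted run does not say which events are equivocal. Delay is permitted, not required.

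A reader might also infer that 4.3.3 contradicts itself. Items 6 and 7 could look like carve-outs from the general Grade 3 rule, and item 1 ("Grade 4 irAE regardless of duration") could seem to clash with item 7, which counts endocrinopathies "that require treatment discontinuation or are not successfully managed with hormonal replacement therapy". The text does not support this. Any listed criterion is enough, the general rule has only two numbered exceptions, and nothing says that failing item 6 or 7 removes DLT status. Under that reading a clinical Grade 4 endocrinopathy is a DLT by item 1, and items 6 and 7 can still recapture events released by the exceptions.

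**Conclusion.** The concern holds in a narrow form. Applied as written, SAP 6.1.1 cannot score the 4-week delay criterion for any participant, and it can miss prolonged Grade 4 neutropenia with onset from Day 21 or 22. It can also miss item 6's 14-day test for onsets from Day 15 where that item decides. Such events are coded 0, and DLTs can be under-counted in the BLRM and the primary endpoint.

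The timing result needs only the documents' own day counts and Protocol 4.3.3's evaluability rule. SAP Table 2 has a different rule, with at least 11 doses per cycle, which does not fit two doses per cycle. The coding of 0 assumes that SAP 6.1.1 is followed literally and that no one uses the discretionary clauses. The documents give no rate for these events, so the frequency is unknown. The model figures rest on assumed priors and show possibility, not expected effect.

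It would go too far to say that every Grade 3 irAE after the second dose is unscorable, because most are DLTs at onset. It would also go too far to say that pending participants must be counted as DLTs. That is a choice between caution and speed which the plan does not settle.

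**What to change.** Amend SAP 6.1.1 as follows.

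1. Set the indicator to 1 when an AE at least possibly related to PF-07209960 has onset within 28 days and meets any Protocol 4.3.3 criterion, using outcome data followed beyond Day 28.
2. At each dose decision, list for the dose level review every participant with a criterion still pending.
3. Treat those participants as equivocal in the weighted BLRM sensitivity run already planned, at the prespecified weight of 0.5.
4. Update the indicator and rerun the BLRM when the criterion resolves.

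This matches the onset wording already in Protocol 4.3.3 and SAP 3.5.1. It costs a few sentences, with occasional later recoding or slower escalation. Compulsory provisional coding as a DLT is not proposed, since it could trigger the 100% step cap or a repeated cohort for an event that then resolves.

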4.3.4. Maximum Tolerated Dose Definition

MTD is defined as a dose with true DLT rate from the target toxicity interval. The target interval for the DLT rate is defined as (0.16, 0.33).

4.3.5. Maximum Feasible Dose Definitions

Not applicable.

4.3.6. Recommended Phase 2 Dose Definition

The recommended dose for further study (which is normally the same as the RP2D) is the dose chosen for further investigation based on Phase 1 dose escalation study results. If the MTD proves to be clinically feasible for long-term administration in a reasonable number of participants, then this dose usually becomes the RP2D. Further experience with the MTD may result in a RP2D lower than the MTD. During escalation and prior to an MTD being reached, the sponsor may choose to advance a lower dose into expansion. This decision must be made based on safety, PK, PD, and/or efficacy. Furthermore, after reaching the MTD, up to approximately 6-12 participants may be enrolled in the lower doses for the purpose of refining the RP2D based on emerging safety data.

Significant AEs considered to be related to the study intervention or treatment under investigation that occur after the DLT observation period will be reviewed in context of all safety data available. That review may result in re-evaluation of the MTD/RP2D for Part 2 expansion cohort.

4.4. End of Study Definition

A participant is considered to have completed the study if he/she has completed all phases of the study, including the last visit.

The end of the study will be the date of the last visit of the last participant or 2 years after the last participant receives their first dose (whichever occurs first) at which point all study participants will need to complete any protocol-specified post-treatment safety monitoring activities before final closure of the study. The study may also be terminated at any time at the discretion of the sponsor.

5. STUDY POPULATION

This study can fulfill its objectives only if appropriate participants are enrolled. The following eligibility criteria are designed to select participants for whom participation in the study is considered appropriate. All relevant medical and nonmedical conditions should be taken into consideration when deciding whether a particular participant is suitable for this protocol.

Prospective approval of protocol deviations to recruitment and enrollment criteria, also known as protocol waivers or exemptions, is not permitted.

Pfizer will review eligibility criteria verified by the investigator or qualified designee to confirm that participants meet study eligibility criteria before they are enrolled into the study. The enrollment approval process will be initiated for a participant after an informed consent document has been signed and the investigator or qualified designee has assessed the participant as eligible. The enrollment approval will be based on review of CRF/system data.

5.1. Inclusion Criteria

Participants are eligible to be included in the study only if all of the following criteria apply:

1. Participants age ≥ 18 years.
 - Refer to Appendix 4 for contraceptive/reproductive criteria for male ([Section 10.4.1](#)) and female [Section 10.4.2](#) participants.
2. Histological or cytological diagnosis of locally advanced/metastatic solid tumor (NSCLC, SCCHN, RCC, UC, OvCa, or MSS CRC).
 - a. At least 1 prior line of therapy for recurrent or metastatic disease, including either standards of care or investigational therapies. Participants must have progressed or relapsed after or be intolerant to standard therapy approved for the specific tumor type. Exception: participants who actively decline available standard of care therapies are eligible upon documentation of their refusal.
 - b. Participants with NSCLC, SCCHN, RCC, or UC must have received prior anti-PD-1/PD-L1 either as monotherapy or in a combination regimen and had experienced radiographic progression.
 - c. Participants with NSCLC must not have known ALK, ROS1, MET exon 14 skipping, RET rearrangement or EGFR mutation.
 - d. Participants who had received prior anti-PD-1 must be ≥ 90 days from their last anti-PD-1 dose. Participants who received prior anti-PD-L1 are not subject to this restriction.
 - e. Participants with OvCa or MSS CRC must not have received prior anti-PD-1/PD-L1 therapy.
 - f. Demonstrated radiographic progression on most recent tumor assessment imaging.
 - g. For Part 2, in addition:
 - a) Participants with NSCLC must have received either ≥ 2 prior lines of therapy including ≥ 1 prior regimen containing chemotherapy and ≥ 1 prior regimen containing anti-PD-1/PD-L1 or a prior regimen of anti-PD-1/PD-L1 in combination with chemotherapy (eg, atezolizumab with chemotherapy). In addition, NSCLC with a BRAF V600E mutation must have also received BRAF inhibitor with or without MEK inhibitor
 - b) Participants with RCC must have received either ≥ 2 prior lines of therapy including ≥ 1 prior regimen containing anti-PD-1/PD-L1 and ≥ 1 prior regimen containing a small molecule kinase inhibitor or a prior regimen of anti-PD-1/PD-L1 in combination with a small molecule kinase inhibitor (eg, pembrolizumab or avelumab with axitinib).
 - c) Participants with UC must have received ≥ 2 prior lines of therapy including platinum-containing chemotherapy and anti-PD-1/PD-L1, or a single regimen

of platinum-containing chemotherapy followed by anti-PD-1/PD-L1 maintenance therapy.

- d) Participants with MSS CRC must have received ≥ 2 prior lines of therapy including treatment regimens containing combinations of pyrimidine analog, oxaliplatin, irinotecan, anti-EGFR (RAS wild type), encorafenib (if BRAF V600E-positive) and anti-HER2 (if HER2-amplified and RAS and BRAF wild type).
- e) Participants with OvCa must have received ≥ 2 prior lines of therapy including at least 1 regimen with platinum-based chemotherapy and progressed on last two consecutive regimens without evidence of clinical benefit.

3. Participants entering the study in ≥ 1 measurable lesion (at least 10 mm in the longest diameter by CT scan/MRI for non-lymph nodes and at least 15 mm in the short axis for lymph nodes) as defined by RECIST version 1.1 that has not been previously irradiated.
4. Must have tumor tissue available for submission to the sponsor:
 - a. Participants enrolled in Part 1 and Part 2 should consent to undergo biopsy during screening (pre-treatment) or be able to provide archival FFPE material containing tumor that is of diagnostic quality and representative of their diagnosed malignancy taken ≤ 1 year prior to study start. If the archival sample is older than 1 year and a biopsy during screening cannot be performed, the investigator must contact the sponsor to discuss eligibility prior to enrollment.
 - b. Participants enrolled in Part 2 dose expansion must have a tumor amenable to biopsy and consent to planned mandatory pre- and on-treatment biopsy procedures until the sponsor deems that an adequate number of participants (10-15 paired fresh biopsies per cohort) have been successfully biopsied, at which point participants will only be required to submit pre-treatment biopsies (either archival tissue or de novo biopsy as above). Special considerations will be made for participants with poorly accessible tumors or deemed medically unsafe as determined by the investigator after discussion and agreement by the sponsor.
5. ECOG PS 0-2 for Part 1, 0-1 for Part 2.
6. Adequate hematologic function, including:
 - a. ANC $\geq 1,500/\text{mm}^3$ or $\geq 1.5 \times 10^9/\text{L}$;
 - b. Platelets $\geq 100,000/\text{mm}^3$ or $\geq 100 \times 10^9/\text{L}$;
 - c. Hemoglobin $\geq 9 \text{ g/dL}$. Limited transfusions to reach this value are allowed, after discussion with the sponsor's medical monitor. There should not be chronic need for transfusions (>1 per month) in the recent (approximately 3 months) past.
7. Adequate renal function, including:
 - d. Estimated creatinine clearance $\geq 50 \text{ mL/min}$ as calculated by Cockcroft-Gault method. In equivocal cases, a 24-hour urine collection test can be used to estimate the creatinine clearance more accurately.

8. Adequate liver function, including:
 - a. Total serum bilirubin $\leq 1.5 \times$ ULN;
 - b. AST and ALT $\leq 2.5 \times$ ULN; $\leq 5.0 \times$ ULN if there is liver involvement by the tumor;
 - c. Alkaline phosphatase $\leq 2.5 \times$ ULN ($\leq 5 \times$ ULN in case of bone metastasis).
9. Adequate coagulation function, including:
 - a. INR or aPTT $\leq 1.5 \times$ ULN.
10. LVEF $\geq 50\%$ by echocardiogram or MUGA.
11. Resolved acute effects of any prior therapy to baseline severity or CTCAE Grade ≤ 1 except for AEs not constituting a safety risk by investigator judgment.
12. Willing and able to comply with all scheduled visits, treatment plan, laboratory tests, lifestyle considerations, and other study procedures.
13. Capable of giving signed informed consent as described in [Appendix 1](#), which includes compliance with the requirements and restrictions listed in the ICD and in this protocol.

5.2. Exclusion Criteria

Participants are excluded from the study if any of the following criteria apply:

1. Known symptomatic brain or leptomeningeal metastases requiring steroids. Participants with previously diagnosed brain or leptomeningeal metastases are eligible if they have completed their treatment and have recovered from the acute effects of radiation therapy or surgery prior to planned first dose, have discontinued corticosteroid treatment for these metastases for at least 4 weeks and are neurologically stable for 3 months (requires MRI confirmation).
2. Any other active malignancy within 3 years prior to enrollment, except for adequately treated basal cell or squamous cell skin cancer, or carcinoma in situ.
3. Major surgery within 4 weeks prior to planned first dose.
4. Radiation therapy within 4 weeks prior to planned first dose.
5. Systemic anti-cancer therapy within 4 weeks prior to planned first dose (6 weeks for mitomycin C or nitrosoureas). If the last immediate anti-cancer treatment contained an antibody-based agent(s) (approved or investigational), then an interval of 28 days or 5 half-life (whichever is shorter) of the agent(s) prior to receiving the study intervention treatment is required. Participants who received anti-PD-1 therapy (but not anti-PD-L1) require an interval of 90 days prior to planned first dose.
6. Active and clinically significant bacterial, fungal, or viral infection, Hepatitis B or Hepatitis C infection at screening (positive HBsAg or positive HCV RNA if anti-HCV antibody test positive), known HIV or AIDS-related illness. HIV seropositive participants, who are in good health and at low-risk for AIDS-related

outcomes, may qualify for inclusion in the study after discussion with the sponsor, but AIDS is exclusionary.

The following criteria for immune status and HIV ongoing therapy must be met for a HIV seropositive participant to be eligible for the study:

- a) Immune status criteria:
 - a. CD4+ T-cell counts ≥ 350 cells/ μ L at the study start;
 - b. No history of AIDS-defining opportunistic infections;
 - c. In general, patients should be eligible if they have not had an opportunistic infection within the past 12 months.
- b) Ongoing HIV therapy criteria:
 - d. Must be receiving recommended concurrent ART treatment according to the guidelines ([AIDSinfo, 2020](#));
 - e. Began ART treatment >4 weeks prior to study start (to ensure ART is tolerated and toxicities are not confused with study drug toxicities);
 - f. HIV viral load <400 copies/mL for >4 weeks prior to study start (to ensure ART is tolerated and HIV controlled).

7. Active COVID-19/SARS-CoV2: Refer to [Appendix 10](#) for further information.
8. Baseline 12-lead ECG that demonstrates clinically relevant abnormalities that may affect participant safety or interpretation of study results (eg, baseline QTc interval >470 msec, complete LBBB, signs of an acute or indeterminate-age myocardial infarction, ST-T interval changes suggestive of active myocardial ischemia, second- or third-degree AV block, or serious bradyarrhythmias or tachyarrhythmias). If the baseline uncorrected QT interval is >470 msec, this interval should be rate-corrected using the Fridericia method and the resulting QTcF should be used for decision making and reporting. If QTc exceeds 470 msec, or QRS exceeds 120 msec, the ECG should be repeated 2 more times and the average of the 3 QTc or QRS values should be used to determine the participant's eligibility. Computer-interpreted ECGs should be overread by a physician experienced in reading ECGs before excluding participants. Cases must be discussed in detail with sponsor's medical monitor to judge eligibility.
9. Any of the following in the previous 6 months: myocardial infarction, long QT syndrome, Torsade de Pointes, arrhythmias (including sustained ventricular tachyarrhythmia and ventricular fibrillation), serious conduction abnormalities (e.g., bifascicular block [defined as right bundle branch and left anterior or posterior hemiblock], 3rd degree AV block), unstable angina, coronary/peripheral artery bypass graft, symptomatic CHF, New York Heart Association class III or IV, cerebrovascular accident, transient ischemic attack, symptomatic pulmonary embolism, and/or other clinical significant episode of thrombo embolic disease. Ongoing cardiac dysrhythmias of NCI CTCAE Grade ≥ 2 , atrial fibrillation of any grade (Grade ≥ 2 in the case of asymptomatic lone atrial fibrillation). If a participant

has a cardiac rhythm device/pacemaker placed and QTcF >470 msec, the participant can be considered eligible. Participants with cardiac rhythm device/pacemaker must be discussed in detail with sponsor's medical monitor to judge eligibility.

10. Abnormal cardiac valve morphology (\geq grade 2) documented by echocardiogram (participants with grade 1 abnormalities [ie, mild regurgitation/stenosis] can be enrolled on study). Participants with valvular thickening should not be enrolled into the study.
11. Anticoagulation with vitamin K antagonists is not allowed. Anticoagulation with low molecular weight heparin and Factor Xa inhibitors or use of antiplatelet therapy is allowed but must be held per institutional requirements for biopsies and whenever platelet count is $<50,000/\text{mm}^3$. If participants are on antiplatelet therapy, they must be able to hold antiplatelet therapy for first week of study treatment without significantly increased risk of cardiovascular events.
12. AEs from prior therapy which have not recovered to Grade ≤ 1 or baseline.
13. Hypertension Grade 3 or higher (eg, $\geq 160/100 \text{ mmHg}$) that cannot be controlled by medications despite optimal medical therapy.
14. Participation in other studies involving investigational drug(s) within 4 weeks prior to first dose.
15. Known or suspected hypersensitivity to any PF-07209960 components, or to mAbs or other therapeutic proteins such as fresh frozen plasma, human serum albumin, cytokines, or interleukins.
16. History of clinically significant Grade ≥ 3 immune mediated AE that was considered related to prior immune modulatory therapy (eg, immune checkpoint inhibitors, co stimulatory agents, etc.) and required immunosuppressive therapy. Patients with immune-mediated endocrinopathies controlled with hormonal replacement therapy (eg, thyroid disorders, diabetes, adrenal insufficiency) are eligible.
17. Active autoimmune disease that might deteriorate when receiving an immunostimulatory agent. Patients with diabetes type I, vitiligo, psoriasis, or hypo- or hyperthyroid disease not requiring immunosuppressive treatment are eligible.
18. Organ transplant requiring immunosuppressive treatment or prior allogeneic bone marrow or hematopoietic stem cell transplant.
19. Current use of immunosuppressive medication at the time of randomization, EXCEPT for the following: a) intranasal, inhaled, topical steroids, or local steroid injection (eg, intra-articular injection); b) Systemic corticosteroids at physiologic doses $\leq 10 \text{ mg/day}$ of prednisone or equivalent; c) Steroids as premedication for hypersensitivity reactions (eg, CT scan premedication).
20. Active bleeding disorder, including gastrointestinal bleeding, as evidenced by hematemesis, significant hemoptysis or melena in the past 6 months prior to first dose.
21. History of interstitial lung disease or pneumonitis.

22. Participants with the presence of any open, active wound.
23. Pregnancy or breastfeeding.
24. Other medical or psychiatric condition including recent (within the past year) or active suicidal ideation/behavior or laboratory abnormality that may increase the risk of study participation or, in the investigator's judgment, make the participant inappropriate for the study.
25. Investigator site staff or Pfizer employees directly involved in the conduct of the study, site staff otherwise supervised by the investigator, and their respective family members.

